All randomizations are conducted intra-hospital (i.e., no cluster randomization), to avoid the confounding effect of practice variation. Randomization will be conducted in blocks of 10 to allow better distribution between groups at each interim analysis. It will be done by the Data Coordinating Center (DCC) and automated in an web-based REDCap data collection instrument. Upon confirmed eligibility and consent, the REDCap will reveal the group assignment to institution's pharmacy, which will then release the drug if the patient is assigned to the intervention group (Group tPA50, Group tPA50+drip). Time zero is assigned as the time of randomization. We anticipate that each of the five centers will enroll 8-12 patients.

The figure below illustrates the initial planned sequential, stepped-wedge design and the proposed new design after the adaptations driven by the first interim analysis. Study will continue during the interim analyses, unless a safety issue occurs.

INITIAL DESIGN

NEW DESIGN AFTER 1st INTERIM ANALYSIS

Re-bolusing of tPA, at the same dose, is permitted in the tPA50 intervention group in those patients who show an initial transient response (>20% improvement of PaO₂/FiO₂ over pre-infusion of alteplase at any of the measurements at 2, 6, 12 or 18 hours, but <50% improvement of PaO₂/FiO₂ at 24 hours after randomization); the repeat dose will be given between 24 and 36 hours after the initial tPA administration.

The same EXCLUSION criteria apply to the second tPA (alteplase) bolus. The heparin drip should be stopped two hours before the second tPA (alteplase) and re-started after the second alteplase infusion ends, at the same dose as before the second alteplase.

Other modifications of the dosing are as follows:

- Fibrinogen monitoring:** For all tPA administration groups, fibrinogen levels will be measured before and after tPA IV bolus, 6 hours after the start of the infusion, then every 6 hours for first 24 hours, and once a day for 6 days following treatment intervention in all the groups (see detailed lab testing schedule below). **If fibrinogen levels fall below 300 mg/dL, the second bolus of tPA (alteplase) is NOT indicated.**

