### 6.4. Outcomes comparison:

All analyses will be conducted initially as an intent-to-treat (patients are analyzed in the group they were randomized to), followed by an as-treated analysis. The primary outcome will be assessed within group and between groups. Differences in the primary outcome will be assessed using linear mixed models, with appropriate transformations if normality departure of residuals is detected. Linear mixed models allows us to adjust for potential confounders detected in the comparison of the groups at baseline using inverse probability weighting by a propensity score, the covariance structure, the repeated measures and the intra-hospital correlation (as this is a multicenter study). In addition, it tolerates missing observations. We will also compare percent change over baseline, using t-tests with the appropriate adjustment for heteroscedasticity if needed. Categorical outcomes will be compared using generalized estimating equations to account for confounders (as above), covariance structure and intra-hospital correlation. In addition, we will compare the “dose” of the intervention (i.e., how much of the treatment the patient received) as the effect of interest, as premature death is, unfortunately, expected. Survival analysis with inverse probability weighted Cox proportional hazards model and robust sandwich variance estimate with clustering for hospitals will be used for mortality and for survivor-bias outcomes censoring for death (e.g., thrombotic complication). As all outcomes are in-hospital, loss to follow-up is not likely. The pre-planned comparisons include within group (improvement over baseline) and between groups, all two-tailed with significance declared as defined by the Pocock spending method.

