### 6.5. Pre-planned subgroup analyses

We anticipate the following subgroup analyses, which will assist in determining whether there is a subgroup of patients for whom the intervention is more beneficial/harmful.

- Baseline PaO2/FiO2 <100 and <50
- Hemodynamic instability with vasopressors
- Age <35, <50, <65 years
- D-Dimers median levels
- Fibrinolysis shutdown (by TEG or ROTEM)
- Fibrinogen median levels
- Prone/supine positioning
- Requirement of re-bolusing of alteplase
- Received dose of alteplase as premature death or adverse event or other reasons may preclude the administration of complete treatment
- Elimination of centers contributing <2 cases.

Additional subgroup analyses may be defined at an interim analysis and will be added for the subsequent interim analyses. This will be documented by filing another version of this SAP with the IRBs, DSMB, funder and FDA.

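### Received dose and re-bolusing are analysed as a treatment effect and as subgroups, although both are partly set after randomisation by the early PaO2/FiO2 course and survival

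*SAP*

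**What the plan says.** SAP 6.4 puts intention-to-treat first, then as-treated. It adds a comparison of the dose of the intervention, defined as "how much of the treatment the patient received", and treats it "as the effect of interest, as premature death is, unfortunately, expected". The Protocol's statistical analysis section plans the same comparison. The only confounder adjustment described is inverse probability weighting for differences between the groups at baseline.

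SAP 6.5 lists two pre-planned subgroups that depend on treatment received: "Requirement of re-bolusing of alteplase" and "Received dose of alteplase as premature death or adverse event or other reasons may preclude the administration of complete treatment". Their stated purpose is to find patients in whom the drug does more good or harm.

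The rules that determine dose are elsewhere:

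- **Second bolus (Protocol, Design):** "Re-bolusing of tPA, at the same dose, is permitted in the tPA50 intervention group in those patients who show an initial transient response". This means a rise of more than 20% "over pre-infusion of alteplase at any of the measurements at 2, 6, 12 or 18 hours", together with less than 50% "improvement of PaO₂/FiO₂ at 24 hours after randomization". The repeat dose falls 24 to 36 hours after the first, the exclusion criteria apply again, and fibrinogen below 300 mg/dL rules it out.
- **Cessation (safety tables in both documents):** triggers include a PaO2/FiO2 fall of at least 30% from baseline, cardiopulmonary arrest, and listed bleeding, neurological and allergic events.
- **Drip arm (SAP 3.1):** the 50 mg bolus, then 2 mg/hr for 24 hours, 48 mg in all.
- **Weight cap (SAP 3.1):** the bolus may not exceed 0.9 mg/kg.

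**The concern.** The primary outcome is PaO2/FiO2 change at 48 hours. The quantity that opens or closes the route to more drug is the same measurement, read between 2 and 24 hours. Dose received is therefore partly an early reading of the outcome, and partly a record of who survived long enough to be dosed. SAP 6.5 itself names death and adverse events as reasons for a short dose.

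Three uses are at stake. The documents say the results should inform a Phase III trial, so an apparent dose-response could steer the next regimen. SAP 3.3 makes absence of effect in any pre-specified subgroup one of its futility conditions, so an artefact in either subgroup could weigh in that decision. And the trial has already reasoned from re-bolused patients: the Protocol's rationale for the drip cites the lack of response to the second bolus. That is an observation in patients selected on their own course, without comparable controls.

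**Working it through.** **1. Is there a randomised contrast?** The plan gives no figure for the dose analyses, so there is none to reproduce; the question is structural. Controls are assigned no alteplase, so no control can require a re-bolus or receive a partial dose. If the crossover provision were used, controls would get drug only after failing to improve, which again depends on outcome. Neither subgroup can compare randomised arms. Weighting on baseline variables cannot balance a characteristic that develops over the following 24 hours. No landmark or time-varying exposure method is specified, and the dose analysis is not labelled exploratory.

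**2. Which way does the selection run?** Take a baseline of 100 for illustration. The second-bolus limits are 100 × 1.20 = 120 (by 18 h) and 100 × 1.50 = 150 (at 24 h); the cessation limit is 100 × 0.70 = 70.

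| Course | Eligible for second bolus | tPA50 dose |
|---|---|---|
| 125 at 6 h, 130 at 24 h | yes | up to 100 mg |
| 125 at 6 h, 155 at 24 h | no, rise is 50% or more | 50 mg |
| 95 at 6 h, 90 at 24 h | no early rise | 50 mg |

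The 50 mg group mixes the best and the poorest courses, so the bias in tPA50 can take either sign. In the drip arm dose is 50 + 2 × (hours of drip), at most 50 + 48 = 98 mg. A fall to 70 found at 12 h, with the drip begun at 2 h, gives 50 + 2 × 10 = 70 mg. There, low dose marks deterioration or death, and the sign is positive.

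**3. How large could it be?** The documents give the rules but not the variability of serial PaO2/FiO2, so these are assumptions. Main set: median baseline 110 with entry below 150; log-scale within-patient SD 0.15-0.35; correlation time 24-72 h; mean natural trend over 48 h of 0 to +0.6 log units; 48-h mortality about 5-16%, higher with a poor course. No drug effect. The second-bolus trigger, the 30% cessation rule and death set the dose, and 48-h change in survivors is regressed on mg received. There were 4,000 trials per setting, with two-sided p<0.05. A to C and F have no natural trend; D has +0.4, E has +0.6; F has the highest mortality.

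Mean 48-h change with an inert drug, %:

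| Setting | tPA50: 100 mg vs 50 mg | Drip: full vs partial |
|---|---|---|
| A | 23.4 vs 13.7 | 25.4 vs −16.7 |
| B | 23.2 vs 4.4 | 15.2 vs −23.5 |
| C | 27.3 vs 21.4 | 33.4 vs −16.2 |
| D | 63.2 vs 79.2 | 77.2 vs 4.1 |
| E | 83.6 vs 124.7 | 114.3 vs −24.6 |
| F | 25.7 vs 17.1 | 28.2 vs −14.6 |

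Trials with p<0.05, %:

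| Setting | tPA50, n=25 | Drip, n=25 | 10 tPA50 + 15 drip | Same + 25 controls at 0 mg | Randomised comparison |
|---|---|---|---|---|---|
| A | 8.2 | 21.8 | 10.0 | 5.0 | 4.4 |
| B | 22.1 | 20.9 | 12.1 | 5.1 | 4.9 |
| C | 6.1 | 21.3 | 8.4 | 4.8 | 5.0 |
| D | 3.3 | 8.8 | 6.4 | 4.0 | 5.0 |
| E | 3.7 | 6.6 | 7.0 | 4.0 | 5.3 |
| F | 6.7 | 16.9 | 9.2 | 5.1 | 5.3 |

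**4. Arm sizes.** SAP 3.1 randomises the first 20 patients to tPA50 or control, about 10 on tPA50, and the other 50 − 20 = 30 to drip or control, about 15 on drip. The 10 + 15 column fits that plan. Twenty-five on tPA50 (the arm size in the SAP sample-size section) arises only if the 50% improvement branch keeps that regimen to the end; 25 on drip exceeds the current plan.

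**5. A second set of assumptions for tPA50** (mean 120, SD 30-45, 24-h autocorrelation 0.5-0.9, natural 48-h rise of 0, 40 or 80, no deaths) gave a mean dose-outcome correlation from about −0.09 to +0.41. p<0.05 occurred in about 3-20% of trials with 10 patients and 3-46% with 25.

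**The case against.** The strongest reply is that this is a supplementary analysis. Intention-to-treat comes first, the dose comparison is introduced as an addition, and the randomised comparison held its level in every setting (4.4-5.3%). That stands, and it limits the severity.

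Second, SAP 6.4 does not say whether controls enter the dose model. At 0 mg in one linear model they bring false positives to 4.0-5.1% in the main simulations and 3-8% under the second set, because the randomised contrast of none against some dominates. That also stands: the inflation belongs to models of treated patients only, and SAP 6.4 is under-specified as much as wrong. It does not rescue the two subgroups, which contain no controls.

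Third, dose has other determinants: assigned regimen, the weight cap (50 / 0.9 = 55.6 kg, below which the bolus is reduced), fibrinogen, bleeding and other cessation events, and the fact that re-bolusing is permitted, not required. The simulations leave these out, so the percentages show possible size only.

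A reader might infer that the plan will show more tPA giving better oxygenation even for an inert drug. The documents do not support that. The 50% ceiling at 24 hours keeps the best early courses on 50 mg; 100 mg looked worse in settings D and E, and some settings show no excess of false positives. The Protocol's own first-stage reading did not favour the second bolus either.

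**Conclusion.** The point holds: dose received and re-bolusing are post-randomisation quantities tied to the early outcome and to survival, and the planned baseline weighting does not address that. It is firmest for the two SAP 6.5 subgroups, which are wrong as written because no randomised contrast exists in them. For SAP 6.4 it holds as an uninterpretable comparison among treated patients.

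The direction is positive in the drip arm and unpredictable in tPA50. The size is uncertain: from no excess to roughly one trial in five at p<0.05 in most of the settings examined, 6.4-12.1% for the planned mix of about 10 tPA50 and 15 drip patients, and as high as 46% in one set of assumptions with 25 on tPA50. All of this rests on assumed variability, autocorrelation, natural recovery and, in the main set, mortality. The mechanism rests on the documents alone. It should be corrected, but it does not threaten the primary analysis.

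**What to change.** Delete re-bolusing and received dose from the SAP 6.5 subgroup list, which also keeps them out of the SAP 3.3 futility condition. Remove dose received as an effect of interest from SAP 6.4 and from the Protocol's statistical analysis section. Compare assigned regimens with control by intention-to-treat, and tabulate doses, early cessations with reasons, and re-bolus rates descriptively. Early death, the reason SAP 6.4 gives for the dose comparison, already enters the randomised comparison through the mortality outcomes.

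If a dose analysis is kept, label it exploratory and non-causal, state whether controls are included, and use a landmark or time-varying exposure method with serial PaO2/FiO2. The landmark has a limit. A re-bolus begun at 36 h and infused over 2 h ends at 38 h, leaving 42 − 38 = 4 to 54 − 38 = 16 hours before the outcome reading, or less if first dosing lagged randomisation. Change counted from a landmark is also no longer change from baseline. Removal is therefore the cleaner option.

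The cost is wording in two documents and the loss of one exploratory comparison. No extra data or patients are needed.

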- 5) the bolus/infusion regimen was employed in the seminal 2001, Hardaway study⁷ demonstrating an improvement in oxygenation in patients with advanced ARDS,

6) the 2mg/ml tPA and 500 U heparin is the standard combination employed by interventional radiology for directed fibrinolysis (personal communication [name], Director of IR, UCSD), and

7) we are reticent to increase the tPA dose to 100 mg considering overall risk: benefit.

The above modification was predicted in the original COMIRB submission, in which we anticipated both dose and mode of administration changes is our adaptive plan.

The rationale and change to a bolus/infusion regimen was discussed with the DSMB, and they concurred without reservation (see letter from DSMB, in which they concur with proposed plan).

[figure not shown]
Design:

This is a multicenter ([name] Shock Trauma Center at Denver Health Medical Center (DHMC), University of Colorado Hospital (UCH), National Jewish Health / St. Joseph Hospital (NJH/SJH), Beth Israel Deaconess Medical Center (BIDMC), Long Island Jewish Hospital / North Shore University Hospital (LIJH/NSUH), Scripps Health (SH), St. Mary's Medical Center (SM), University of Miami (UM), Ben-Taub General Hospital (BT) and Dallas Methodist (DM)) Phase IIa clinical trial. The design is a pragmatic, open label, randomized, controlled, rapidly adaptive clinical trial, with 3 interim analyses and 1 final look at the data. For rapid efficacy assessment to isolate the arm(s) with the highest likelihood of success and lowest bleeding risk, we will deploy each intervention arm sequentially up to each interim analysis, in a modified stepped-wedge fashion, with pre-planned adaptations (below) at each interim analysis. Pre-planned adaptations described below will be contemplated at each interim analysis or earlier if recommended by the Data Safety Monitoring Board (DSMB).

[figure not shown]

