### 3.2. Sample size

We anticipate that each of the five centers will enroll 8-12 patients. Sample size and power Analysis was conducted using Pass, vs 14.0 (NCSS, LLC, Kaysville, Utah, USA) and focused on the primary outcome as defined above.

Sample size assumptions:

- power=80%, confidence=95%, and 4 sequential tests(3 interim+1 final), using the Pocock spending function to determine test boundaries,
- potential improvement assumptions based on a previous study 40 with appropriate(e.g., Denver) altitude correction as well as mean baseline PaO2/FiO2=149 with an overestimated standard deviation of 100,
- design effect=1.12 due to the study's multicenter nature (intra-class correlation coefficient=0.03, average cluster=5);
- ~20% inflation to account for premature death

---

 Urbaniak, G. C., & Plous, S. (2013). Research Randomizer (Version 4.0) [Computer software]. Retrieved on April 10, 2020, at <http://www.randomizer.org/>

A sample size of 50 (25 in each intervention group and 25 in the control group) patients detects a >70% improvement in PaO2/FiO2 between intervention groups (both tPA50 and tPA 50 plus drip) and controls, and >91% improvement in PaO2/FiO2 between intervention tPA 50 plus drip) and controls. Recruitment will assume at least 30% increase to account for refusal or inability to consent.

**Consent: We anticipate consenting enough patients to result in 50 eligible patients, thus we plan on a max of 60, to be re-evaluated during each of the interim analyses. LAR, as defined by the state and institutions legislation/policies, will be able to consent.**

The table below shows the details of the interim analyses with the Pocock spending method:

Look	N of Patients	Lower Bndry	Upper Bndry	Nominal Alpha	Inc Alpha	Total Alpha	Inc Power	Total Power
1	10	-2.43798	2.43798	0.015	0.015	0.015	0.18976	0.190
2	20	-2.42677	2.42677	0.015	0.011	0.026	0.25179	0.442
3	30	-2.41014	2.41014	0.016	0.009	0.035	0.21191	0.653
4	50	-2.39658	2.39658	0.017	0.008	0.043	0.14655	0.800

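### Clustering the sandwich variance on only 5 to 10 hospitals makes tests of common secondary outcomes, such as mortality, reject too often; a patient-level or hospital-stratified analysis avoids this

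*SAP*

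**What the plan says.** SAP 6.4 assigns mortality, and outcomes censored at death such as thrombotic complications, to an inverse-probability-weighted (IPW) Cox model with a "robust sandwich variance estimate with clustering for hospitals". For the rest, "Categorical outcomes will be compared using generalized estimating equations" that take account of hospital correlation; the statistical analysis section of the protocol likewise makes the hospital the clustering unit. The sandwich wording belongs to the Cox sentence. No variance estimator is named for GEE.

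The number of hospitals is given in three ways:
- The protocol, and again SAP 3.2 (Sample size): "We anticipate that each of the five centers will enroll 8-12 patients".
- The protocol's Design paragraph lists ten sites, two of them written as hospital pairs; the list ends "Ben-Taub General Hospital (BT) and Dallas Methodist (DM)) Phase IIa clinical trial".
- SAP 3.2 (Sample size) assumes "design effect=1.12 due to the study's multicenter nature (intra-class correlation coefficient=0.03, average cluster=5", which with 50 patients implies ten clusters.

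Comparisons are "all two-tailed with significance declared as defined by the Pocock spending method", and the boundary table in SAP 3.2 is printed on the z scale. Neither document mentions a small-sample correction, a t or F reference, or an exact or permutation test for these analyses.

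**The concern.** A sandwich variance clustered on hospital estimates its middle term from one residual contribution per hospital. It is justified when hospitals are many. With 5 or 10 it is biased downward, because fitted residuals are too small, and it is itself very noisy. A normal reference ignores both problems.

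The outcomes at stake are 14- and 28-day mortality, successful extubation, oxygenation response and survival to discharge. Their intervals would be too narrow in a plan that says (Protocol, after the sample size section; SAP 3.2) that interpretation, and the step to Phase III, will rest on effect sizes with confidence intervals. Efficacy stopping (SAP 3.3) also requires at least one secondary outcome to reach significance, and SAP 4.2 declines any multiplicity adjustment.

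**Working it through.** **Inputs from the documents.** N = 50, from "A sample size of 50 (25 in each intervention group and 25 in the control group", simulated as 25 tPA against 25 control; ICC 0.03 and average cluster 5 (SAP 3.2); 5 or 10 hospitals (above); two-sided tests; final boundary 2.39658 with nominal alpha 0.017, taken as printed in the SAP 3.2 table; patients randomised within hospital (SAP 3.2, Randomization details); mortality 22-64% (protocol abstract).

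**The plan's own clustering figure.** Design effect = 1 + (m - 1) x ICC = 1 + (5 - 1) x 0.03 = 1.12. It reproduces exactly.

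**Rough analytic check.** The noise in the variance estimate alone makes the ratio of estimate to standard error behave roughly like t on K-1 df. Comparing it with normal limits gives:
- K = 5: P(|t4| > 1.96) = 0.122; P(|t4| > 2.39658) = 0.075.
- K = 10: P(|t9| > 1.96) = 0.082; P(|t9| > 2.39658) = 0.040.

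**Simulation under no treatment effect.** About 1:1 allocation within hospital, ICC 0.03 (0.10 as sensitivity), event rates 20% and 45%, 4,000 runs per cell, hospital sandwich with normal reference, no IPW:

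| Hospitals | Mean SE / true SD | GEE, nominal 5% | Cox, nominal 5% | GEE, at 2.397 | Cox, at 2.397 |
|---|---|---|---|---|---|
| 5 equal | 0.81-0.86 | 11.9-15.1% | 13.3-14.5% | 6.3-9.5% | 7.2-8.9% |
| 10 equal | 0.91-0.92 | 6.6-9.1% | 6.5-9.2% | 2.5-4.4% | 2.2-4.6% |
| 10 unequal | 0.85-0.88 | 9.1-10.8% | 8.6-11.0% | 4.8-5.6% | 4.3-5.8% |

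Standard errors in this grid are therefore about 8-19% too small; further runs widen that to 7-21%. A further set of Cox runs across 22-64% event rates gave 14.5-14.9% with 5 hospitals and 7.1-11.0% with 10. GEE with an exchangeable working correlation gave 13.4-14.8% and 7.5-9.0%.

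**With IPW** for covariates with |SMD| > 0.2: 11.0-13.2% with 5 hospitals and 6.0-9.0% with 10. In one Cox cell (10 equal hospitals, 45% events) the mean standard error was not too small (ratio 1.02).

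**Interim looks** (GEE, no IPW): with 5 hospitals the inflation is already present at n = 20 (9.4-13.3%) and n = 30 (9.8-13.4%). With 10 hospitals at n = 20 there was none (2.8-5.2%).

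**Rare outcomes.** The documents give no rate for 48-hour mortality or thrombosis; 5% and 10% are assumptions. With 10 hospitals, rejection among estimable data sets was 0.8-2.5%, and 14-52% of data sets gave no usable estimate. With 5 hospitals it was 4.5-7.3%, with 14-54% unusable.

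**Alternatives.** Nominal 5%, common outcomes:
- Same sandwich with t(K-1): 3.1-6.5%, and 3.6-7.1% in the further Cox runs.
- GEE with Mancl-DeRouen correction and t(K-1): 1.7-3.5%.
- Cox with patient-level robust variance and normal reference: 2.3-5.0%.

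**The case against.** A reader might infer that every categorical, mortality and thrombosis test rejects too often. The documents do not support that. They give no rates for thrombosis or 48-hour death, and if these are rare the tests at ten hospitals are conservative or cannot be computed.

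A reader might also take the sandwich wording to cover GEE. It does not: the robust variance is only the usual default there, so for GEE the defect is an omission. Nor does the SAP state a normal reference outright; the z-scale boundaries make it the natural reading.

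The five-hospital figures rest on one repeated sentence, while the site list and the average cluster of 5 both point to ten. That is fair, and the ten-hospital figures are smaller. But SAP 6.5 plans an analysis dropping centers with fewer than two cases, so uneven enrolment is foreseen, and the unequal row (8.6-11.0%) is then more relevant than the equal one.

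It is also tempting to say that the error spreads to the trial's decisions. Mostly it does not. The primary outcome uses linear mixed models and t-tests. The n = 20 adaptation thresholds (P/F change, dead space, ICU- or ventilator-free days) are observed differences, not p-values. Efficacy stopping needs the primary outcome as well, so an inflated secondary test cannot raise the false-stop rate above that of the primary alone; it only weakens the added requirement.

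Finally, IPW is part of the Cox analysis and usually lowers the inflation. It lowers it without removing it.

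**Conclusion.** The concern holds for common secondary outcomes. Following the stated Cox method with 5 to 10 hospitals and a normal reference gives, without IPW, standard errors about 7-21% too small. Type I error at nominal 5% is then about 12-15% with 5 hospitals and 6.5-11% with 10. At the printed final boundary (nominal 1.7%) it is about 6-10% and 2-6%. With IPW the nominal-5% figures are about 11-13% and 6-9%. The same sizes apply to GEE if the default robust variance is used.

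This rests on N = 50, ICC near 0.03, near-balanced allocation within hospital, event rates of roughly 20-64% and a normal reference. It does not extend to rare outcomes, the primary outcome or the adaptation thresholds, and it reaches efficacy stopping only through the required secondary outcome.

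**What to change.** In SAP 6.4, use analyses that do not need many hospitals; within-hospital randomisation makes them legitimate.

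- **Mortality and outcomes censored at death:** Cox with a patient-level robust variance, or stratified by hospital.
- **Categorical outcomes:** Mantel-Haenszel or conditional analysis stratified by hospital.
- **If the hospital sandwich is kept:** state the number of hospitals K, name the variance estimator for GEE as well, and use a t reference on K-1 df. Adding the Mancl-DeRouen correction is valid but conservative (about 2-3.5%).
- **Sparse events:** state what will be reported when a model cannot be estimated.

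**Cost.** The first two options need a sentence or two and lose little precision. A stratified analysis does lose hospitals whose patients are all in one arm, which matters most at the looks of 10 and 20 patients; the patient-level variance avoids that. Keeping the sandwich with t(K-1) costs more: 95% intervals widen by 2.776/1.960 - 1 = 42% at 5 hospitals and 2.262/1.960 - 1 = 15% at 10. The critical value matching the printed final boundary rises from 2.397 to 3.97 (66%) or 2.94 (23%).
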